Additional inclusion/exclusion criteria include the following: Eligible individuals must achieve a score of 4 or greater on the Auditory Verbal Comprehension Score, which is a subtest of the Western Aphasia Battery-Revised (WAB-R) for full enrollment/participation in the study. Eligible individuals must also name 1-146 of the 176 items correctly on the initial administration of the naming assessment for full enrollment/participation in the study. Individuals who name 0, or greater than 146 items will be excluded. These criteria will be assessed at the initial study visit, after informed consent has been obtained.

b. Source of subjects and recruitment methods

Individuals with aphasia will be recruited by referral from physicians, speech-language pathologists, and neuropsychologists. We will mail and email recruitment letters to neurologists and speech pathologists in the greater Boston area. Interested professionals will describe the study to the potential participants and ask them to contact the researcher if they are interested in participating in the experiment.

Individuals with aphasia will also be recruited from the MGH Institute of Health Professions Aphasia Center. SLPs will share study flyers with individuals with aphasia and ask if individuals are interested in meeting a member of the research team to learn more about the study. If they express interest, a member of the research team will be invited to come to the end of an upcoming scheduled therapy session to talk more about the study, or Aphasia Center staff can coordinate a meeting between the individual and a member of the study staff. It will be clearly communicated that the treating Speech language pathologist has no affiliation to the research study and that expressing or not expressing an interest to speak to research staff, in no way impacts the therapy services they receive in the MGH IHP Aphasia Center.

In addition, individuals with aphasia will be recruited via word of mouth, flyers, flyers/presentations at local aphasia centers, and emails to community health centers and via listservs (the American Speech-Language Hearing Association (ASHA) Special Interest Group 2 Neurogenic

Communication Disorders listserv, as well as the ASHA Special Interest Group 14 Cultural and Linguistic Diversity listserv). We will also recruit via Rally and the MGH IHP IRB-approved Recruitment Database.

IV. SUBJECT ENROLLMENT

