- General Health Questionnaire-12³⁵,
- Stroke and Aphasia Quality of Life Scale⁴¹,
- Subtests of the Cognitive Linguistic Quick Test-Plus (CLQT+)³⁹,
- The Metalanguage in Aphasia Assessment⁴⁰ (MetAphAs),
- The Communication Confidence Rating Scale for Aphasia (CCRSA),
- The Scenario Test⁸⁶

All assessments will be administered via paper and pencil, unless the participant is participating remotely. If they participate remotely, a fully encrypted device will be utilized but all responses will still be collected via paper and pencil.

b) Naming assessments and connected speech probes: Participants will complete three pretreatment naming assessments to establish a stable baseline⁸³ (*Figure 1*). During each baseline session, participants will complete a 176-item naming assessment and one connected speech probe. The 176-item naming assessment has objects from eight categories: animals, clothing, fruits and vegetables, occupations, household objects, other foods, tools. and transportation^{37,45,51}. Participants will be asked to name each object. To elicit connected speech, we will ask participants to verbally describe a picture, weekly activity, and/or personal memory (e.g., Tell me all about your weekend). Naming assessment and connected speech probe coding: We will calculate naming accuracy from the naming assessments and transcribe participants' prenaming verbalizations in order to later analyze and characterize their pre-treatment naming attempts. We will also transcribe and analyze participants' connected speech samples using Correct Information Unit (CIU) analysis⁶⁴, which provides measures of communicative efficiency and informativeness. Treatment and naming probe object selection: Participants' performance on the three pre-treatment naming assessments will determine which objects are either: trained during treatment, included in weekly naming probes, or untrained and used to test for deneralization post-treatment. Any objects a participant is unable to name on one, two, or three assessments will be included in the participant's object list. Of the included objects, we will create separate treatment and naming probe object lists taking into account the objects' semantic category and complexity.

Phase 2: Treatment

Each treatment session will have three sections:

- Strategy Education (~ 15 minutes),
- Naming Treatment Plus Strategy Application (~40 minutes),
- Strategy Debrief (~15 minutes).

Strategy Education. The clinician will:

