Phase 4 post-treatment tests of retention: Participants will attend two additional post-treatment sessions one month and two months after treatment completion to evaluate retention. During these study visits, participants will complete naming assessment and a connected speech connected speech task in which we will ask participants to verbally describe a picture, weekly activity, or personal memory description (e.g., *Tell me all about your weekend*).

- b. Drugs to be used: N/A
- c. Devices to be used: N/A
- d. Procedures/surgical interventions: N/A

e. Data to be collected and when data is to be collected

Pre- and post-treatment data: All pre-treatment and post-treatment cognitive-linguistic assessment data will be collected during pre- and post-treatment assessment sessions. This data will be collected on each respective assessment material's proper test booklet. Data from pre- and post-treatment naming probes will include naming accuracy and circumlocution attempts (i.e., naming attempts). Data from pre- and post-treatment spontaneous speech probes will include verbatim transcriptions of each participant's responses to the spontaneous speech probes (e.g., *Tell me all about your weekend*). Naming and spontaneous speech probe data will be collected

during the three pre-treatment and six post-treatment sessions. Audio recordings of naming probes will be randomized and coded for accuracy.

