b. Study endpoints. The participant's participation with the study will end when they request to withdraw from the study, or after the post-treatment assessments have been completed, whichever occurs first.

c. Statistical methods.

We will use visual inspection⁶⁸, mixed-effects modeling, and effect size calculations to analyze all results. For visual inspection, we will use the conservative dual-criterion method^{20,27,82}. We will use mixed-effects modeling to estimate the extent to which treatment-specific factors (fixed effects), pre-treatment cognitive-linguistic measures (random effects), and participant-specific factors (random effects) explain post-treatment naming and connected speech outcomes. We will calculate effect sizes by subtracting a participant's average pre-treatment score from their average post-treatment score and dividing by the pre-treatment standard deviation⁸.

Aim 1a. Measure PWAs' naming accuracy for trained and untrained objects. We will calculate effect sizes to measure the effect of treatment on participants' naming accuracy for trained objects, untrained semantically-related objects, and untrained semantically-unrelated objects between pre- and post-treatment. Hypotheses: Consistent with prior studies, we expect that naming treatment will yield medium to large effects for trained objects. Additionally, we hypothesize that strategy training will result in an increase in circumlocution-facilitated naming for untrained unrelated objects and yield medium effects for all untrained objects, regardless of semantic relatedness.

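### Aim 1a judges generalization by effect sizes that, at the same gain, grow with the number of objects in a set; set sizes are unstated and no contrast between sets is specified

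*Combined protocol and SAP*

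**What the plan says.** The statistical methods (VI.c) define the effect size as "subtracting a participant's average pre-treatment score from their average post-treatment score and dividing by the pre-treatment standard deviation". Aim 1a applies it to "naming accuracy for trained objects, untrained semantically-related objects, and untrained semantically-unrelated objects between pre- and post-treatment". The hypothesis is that treatment will "yield medium effects for all untrained objects, regardless of semantic relatedness". The section gives no numeric cut-off for medium and does not say over which scores the SD is taken. "Participants will complete three pretreatment naming assessments to establish a stable baseline" (V.a, Phase 1(b)), so an SD taken over a set's own baseline scores rests on three values.

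The sets are built per participant. Entry requires that a person "name 1-146 of the 176 items correctly on the initial administration" (III.a). For the object list, "Any objects a participant is unable to name on one, two, or three assessments will be included" (V.a, Phase 1(b)). Treatment and probe lists are then drawn up with regard to semantic category and complexity. No set size and no equal-size rule is given.

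VI.c also announces visual inspection and mixed-effects models for all results. The model terms it describes are treatment-phase data as fixed effects, with pre-treatment cognitive-linguistic measures and participant characteristics as random effects. None of them is object set. Normalized change is planned for overall improvement, not by set.

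**The concern.** Generalization to objects unrelated to the trained ones is the reason for the study (I.b, I.c). The plan assesses it by asking whether each untrained set shows a medium effect. If the yardstick for each set is that set's own session-to-session SD, it depends on how many objects the set holds, because accuracy over many objects varies less from session to session than accuracy over few. Two sets with the same real gain can then receive different labels, and sets with different real gains can receive the same one. The same applies between participants whose sets differ in length. Nothing specified in VI.c would show whether an apparent difference between sets reflects learning or object count.

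**Working it through.** The plan states no set size, SD or numeric effect, so it has no figure of its own to reproduce. The check applies its formula to assumed inputs.

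**Inputs from the document.** Effect size d = (mean post - mean pre) / pre-treatment SD (VI.c). Three baseline scores (V.a, Phase 1(b)). Objects missed at the first administration: 176 - 146 = 30 at the entry ceiling and 176 - 1 = 175 at the entry floor (III.a). Because one miss in three assessments is enough, each participant's eligible pool is at least that large.

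**Assumptions.** Baseline accuracy 40%. Objects vary independently between sessions, with average within-object variance v between 0.12 and 0.24 (0.24 = 0.4 x 0.6). Session drift t is shared by all objects: 0, 3 or 10 points. Gain 10 points. Set sizes of 10 and 60 objects are illustrative.

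**Formula.** SD of a set's accuracy = sqrt(v/n + t^2), and d = 0.10/SD. Example: v = 0.24, n = 10, t = 0 gives SD = sqrt(0.024) = 0.155 and d = 0.65.

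| Drift t | d, 10 objects (v = 0.24 / 0.12) | d, 60 objects (v = 0.24 / 0.12) | Ratio (v = 0.24 / 0.12) |
|---|---|---|---|
| 0 | 0.65 / 0.91 | 1.58 / 2.24 | sqrt(6) = 2.4 |
| 3 points | 0.63 / 0.88 | 1.43 / 1.86 | 2.25 / 2.11 |
| 10 points | 0.54 / 0.67 | 0.85 / 0.91 | 1.56 / 1.35 |

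**Score scale.** Scoring by counts changes nothing. Gain and SD are both multiplied by n, so d is the same.

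**With an SD from only three baselines.** 100,000 participants were simulated with three pre and three post scores, accuracy rising from 30% to 45% in both sets, and sets of 20 and 80 objects. (Three post scores is an assumption; V.e speaks of data collected "during the three pre-treatment and six post-treatment sessions".)

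| Drift | Median d, 20 objects | Median d, 80 objects | Larger set has larger d |
|---|---|---|---|
| 0 | 1.72 | 3.46 | 77% |
| 5 points | 1.53 | 2.47 | 69% |
| 10 points | 1.20 | 1.55 | 60% |

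With equal sets of 40 objects the last column is 50%.

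**Reversal.** An 80-object set gaining 10 points against a 20-object set gaining 15 points has the higher median d without drift (2.29 against 1.67) and at 5 points (1.63 against 1.51), but not at 10 points (1.02 against 1.19).

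**The same comparison on other scales.** With 30% to 45% in both sets, the raw gain is 15 points in each, a difference of 0. The odds ratio is (0.45/0.55)/(0.30/0.70) = 1.91 in each, so their ratio is 1.0 for 20 or 80 objects. Without drift, d from the known SD is 0.15/sqrt(0.21/20) = 1.46 against 0.15/sqrt(0.21/80) = 2.93.

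**The case against.** The strongest reply is that unequal sets are possible but not documented. If related and unrelated sets were matched in size within each participant, the between-set artefact would vanish, and one common SD on the proportion scale would largely remove it. That stands as a limit on what can be claimed. It does not remove the point, because the plan specifies neither, and matching within a participant would not make effect sizes comparable between participants with lists of different length.

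Shared session drift also weakens the effect, as the tables show, and its size is unknown.

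The hypothesis is that each untrained set reaches medium, not that related and unrelated gains are equal. That is correct, so the absence of a contrast does not leave a stated equality claim untested. Set size still bears on whether each set reaches the label.

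The announcement of mixed models for all results could accommodate an object-set term, but none is described.

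Three stronger readings are tempting:

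- A reader might infer that the sets are unequal by design. The document is only silent on their sizes.
- A reader might turn the 30 and 175 missed objects into a fixed inflation factor for severe over mild participants. The eligible pool is not an analysed set, and 30 is only a lower bound. If objects were equally difficult and independent, 1 - (146/176)^3 = 43% of 176, about 75 objects, would be missed at least once. A participant who names 1 object of 176 also does not share the baseline accuracy, and hence the variance, of one who names 146.
- A reader might infer that the analyses involving aphasia severity are distorted. VI.c models post-treatment naming and connected speech outcomes and does not say that the standardized effect size is the dependent variable.

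**Conclusion.** The concern holds as a gap in specification. On the natural reading of the SD, the planned effect size depends on object count: roughly with the square root of the count when drift is small, and less as drift grows. Between 10 and 60 objects, the same gain gives effect sizes differing by a factor of 2.4 with no drift and about 1.35-1.56 with 10 points. These figures rest on assumed set sizes, item variance and drift, because the document gives none of them. Set size can therefore influence whether a set is called medium and whether sets or participants seem to differ. The document does not show that it will do so in a particular direction. The change is worth making before analysis because it is cheap and concerns the study's main generalization question.

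**What to change.** 1. Report the number of objects in each set for each participant, and state which SD is the divisor.
2. For Aim 1a, add an object-level logistic mixed model of correct or incorrect naming on phase, set (trained, untrained related, untrained unrelated) and their interaction. Include object random effects and participant random intercepts, with participant slopes for phase and set as far as the data allow. Intercepts alone could make the interval too narrow.
3. Report each set's gain in percentage points, and the related-minus-unrelated difference in gain with its 95% interval. State beforehand that a wide interval or a non-significant difference is not evidence of equal generalization.
4. Keep the standardized effect sizes as within-participant description for comparison with the literature. Do not compare them across sets or participants with different object counts.

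The cost is SAP text and one model. No new data are needed, because "During each baseline session, participants will complete a 176-item naming assessment and one connected speech probe" (V.a, Phase 1(b)), the naming assessments are repeated after treatment, and accuracy is already coded. The downside is that the model will probably be imprecise with about ten completers (VI.d), and the headline result will be less directly comparable with published effect sizes.

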We predict that a treatment approach that incorporates restorative, compensatory, and strategy training components would greatly improve generalization in PWA. Therefore, we propose a treatment protocol that involves: (1) a restorative component aimed at improving PWAs' naming ability, and (2) a strategy training component aimed at improving generalization of a compensatory verbal behavior. In the proposed study, the restorative treatment component will be Semantic Feature Analysis ^{11,12,50,93} (SFA), a well-regarded naming treatment. The compensatory behavior will be circumlocution, a verbal behavior in which PWA describe an object's features if they are unable to name it². Circumlocution is known to facilitate naming²⁹ and assist listener comprehension^{3,29,84}. The features PWA often produce when circumlocuting overlap with many of the features included in SFA. The strategy training component will consist of explicit teaching about when and how to use circumlocution, and practice applying it in moments of naming difficulty. We believe that strategy training will aid in PWAs' consistent and effective adoption of circumlocution as a compensatory behavior to facilitate naming and improve listener comprehension. The results of this study are expected to demonstrate that incorporating strategy training into naming treatment has the power to promote generalization of impairmentand participation-level gains in aphasia. Quick identification of naming difficulty and use of circumlocution will lead PWA to spend less time searching for specific words (improved efficiency) and more time producing informative speech (improved informativeness), which will increase their ability to confidently participate in conversation.

II. SPECIFIC AIMS

Aim 1. Evaluate the effectiveness of naming treatment that incorporates strategy training on naming outcomes. Approach: We will administer a 176-item naming assessment pre- and post-treatment.

1a. Measure patients' naming accuracy for trained and untrained objects. Hypothesis: Consistent with prior studies, we expect that naming treatment will yield medium to large effects for trained objects^{55,66,70}. Additionally, we hypothesize that strategy training will result in an increase in circumlocution-facilitated naming for untrained objects, and yield medium effects for untrained objects.

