- (a) provide education on object naming,
- (b) work with the participant to develop strategies to quickly identify instances in which they are unable to name an object,
- (c)teach the participant to immediately begin generating feature words, i.e., circumlocuting, once they realize they are unable to name an object, and
- (d1) teach the participant the six types of feature words they can produce during circumlocution (i.e., the six SFA framework components, Figure 2 below). The clinician and the participant will work together to learn and memorize the six components. Once the participant is able to independently identify four of the six components across three sessions, *Strategy Education* will change as follows.

- The clinician will review steps (a c) and then,
- (d2) ask the participant to list the components. The clinician will provide reinforcement and cues for any strategy components the participant is unable to independently identify. The clinician will also ask the participant to describe any recent instances in which they had success using the strategy at home or out in the community.

Figure 2. Semantic Feature Analysis chart with the six strategy components

Naming Treatment Plus Strategy Application.

- (e) The clinician will place a picture of an object from the treatment list in front of the participant and ask whether the participant can name it. If the participant says no, the clinician will ask them what they should do next (circumlocute) and encourage them to do so. If the participant says yes, they will name the object and the clinician will ask the participant what they would have done *had they been unable* to name it (circumlocute) and encourage them to do so.
- (f) The clinician will encourage the participant to provide as many features as they can during circumlocution. This step engages the participant in *independent feature generation*, identified as the "active ingredient," of SFA³⁷.
- (g) The clinician will ask the participant to identify which of the strategy's components their description included (e.g., If they described a **dog** as, "an **animal** that **barks**," they would identify their description as having included the **category** and **action** strategy components). This step reinforces their knowledge of the strategy's components.

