- (h) The clinician will ask the participant to identify which of the strategy's components were **not** included in their description (in this example, *description, location, association,* and *function*), and to generate one additional descriptive feature using the remaining strategy components. This step reinforces the strategy's components and gives the participant

additional opportunities for independent feature generation. The clinician will give the participant another opportunity to name the object if they had been unable to name it during **(e)** above.

This process (e - h) will be repeated for approximately eight treatment objects (~5 minutes per object). Alternate methods. If/when a participant is unable to independently produce any feature words about an object, the clinician will provide cues to guide them. Cues will be given from least to most facilitative, starting with general questions (e.g., *What does it do?*), to a binary choice (e.g., *Does it bark or meow?*), and eventually providing the correct feature response (e.g., *It barks.*)³⁷.

Strategy Debrief. The final portion of the session will include a debrief, which is regarded as a critical step in the learning process and enables learners to gain insight from direct experience and apply it to future situations^{52,77}.

- (j) The clinician will ask the participant for their reaction and opinion about the treatment session.
- (k) The clinician will provide positive reinforcement²⁶ by describing at least two instances during *Naming Treatment Plus Strategy Application* in which the participant effectively applied the strategy.
- (I) Finally, the clinician and participant will identify opportunities at home in which the participant could envision employing the strategy. The purpose of the debrief is to reinforce the strategy's applicability in all environments.

Phase 3 Post-treatment re-administration of assessments: Participants will complete the same cognitive-linguistic assessments, naming probes and spontaneous speech probes as they did pre-treatment within 20-30 days following the last treatment session.

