Aim 1b. Determine whether PWA learn the strategy and consequently demonstrate a change in their language behavior in moments of naming difficulty. Analyses: We will use visual inspection to examine participants' identification of the strategy components from Treatment Week 2, to Week 8, to post-treatment sessions. We will calculate effect sizes to measure the effect of treatment on the total number of feature words produced during naming assessments and on the average number of feature words produced per naming attempt during assessments, from pre- to post-treatment. Hypotheses: We expect that strategy training will result in participants' ability to identify all six strategy components by Week 8 and at least four of the strategy components during maintenance/retention sessions. We also hypothesize that strategy training will lead PWA to produce more feature words (i.e., engage in circumlocution) during moments of naming difficulty. Specifically, we expect to find medium to large effects on the number of feature words PWA produce during naming attempts.

Aim 2. Evaluate the effect of strategy training on patients' language production during connected speech. Statistical Analyses: We will calculate effect sizes to measure the effect of treatment on number of object words, feature words, CIUs, and CIUs/minute participants produce during connected speech tasks. Hypotheses: We hypothesize that strategy training will lead PWA to produce more object and feature words during connected speech. We expect medium to large effects on object words, feature words, CIUs, and CIUs/minute during connected speech from pre- to post-treatment.

Additional analyses: We will create mixed-effects models using treatment-phase data (e.g., strategy component identification) as fixed effects, and pre-treatment cognitive-linguistic measures (e.g., CLQT+ results) and participant characteristics (e.g., aphasia severity) as random effects to further understand post-treatment outcomes. We will calculate normalized change scores to measure participants' overall improvement relative to their baseline performance and maximum possible change⁵⁶. We will report changes between participants' pre- and post-treatment WAB-R Aphasia Quotient⁴⁶ scores using the benchmarks proposed by Gilmore and colleagues³³.

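### Aim 1b pools feature words over trained and untrained objects, so a change cannot be read as item learning or as use of the strategy on new objects

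*Combined protocol and SAP*

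**What the plan says.** VI.c, Aim 1b, sets two feature-word outcomes, with effect sizes taken from before to after treatment: "total number of feature words produced during naming assessments and on the average number of feature words produced per naming attempt during assessments". The hypothesis attached to them is "we expect to find medium to large effects on the number of feature words PWA produce during naming attempts". Neither this text nor the statement of Aim 1b in II (Specific Aims) divides the objects into sets.

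Aim 1a, in the same section, does divide them. It takes effect sizes on "naming accuracy for trained objects, untrained semantically-related objects, and untrained semantically-unrelated objects", but for naming accuracy only. Its hypothesis expects more "circumlocution-facilitated naming for untrained unrelated objects", yet no feature-word measure by object set is attached to that hypothesis. The mixed-effects models in VI.c name treatment-phase data, cognitive-linguistic measures and participant characteristics. They contain no term for whether an object was trained.

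On the objects themselves, II says "We will administer a 176-item naming assessment pre- and post-treatment". V.a, Phase 1(b), draws the trained objects, the weekly-probe objects and the objects held out to test generalization from that assessment. In Phase 2, for each object worked on, step (f) has the clinician "encourage the participant to provide as many features as they can during circumlocution". Steps (g) and (h) have the participant label those features and add to them. If the participant can produce none unaided, cues escalate, "eventually providing the correct feature response" being the last level.

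**The concern.** Feature words are both the outcome of Aim 1b and the material practised on the trained objects. When a participant gives features for a trained object after treatment, they may be using the strategy, recalling what was rehearsed for that object, or both. On an untrained object only the first explanation is readily available. A count that pools the two kinds of object cannot tell them apart.

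This matters because the trial is about generalization. The background (I.b) faults compensatory treatments for producing gains that stay within treatment. There is one arm and no randomization, so the contrast between trained and untrained objects is the main within-participant means of judging what produced a change. Aim 1a uses that contrast and Aim 1b does not.

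**Working it through.** **The documents' own arithmetic.** Three sessions a week for eight weeks is 3 x 8 = 24 sessions at most. At about eight objects a session that is up to 24 x 8 = 192 object practices. The length of the trained list is not stated, so practices per object cannot be given. With about eight objects a session, it cannot be assumed that every trained object is rehearsed every time. The plan gives no numerical benchmark for a medium or large effect, so there is no stated figure to reproduce.

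**Can pooling mislead, and in which direction?** Every input in this illustration is assumed. Take 88 objects that are hard to name, a share p of them trained, and 0.5 feature words per hard object at baseline. After treatment a fraction u of the trained objects is still unnamed, each with e extra rehearsed features; the trained objects now named carry none. Nothing changes on untrained objects.

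- Baseline total: 88 x 0.5 = 44.
- Total after treatment: 44 + 88p[u(0.5 + e) - 0.5]. It rises only if u(0.5 + e) exceeds 0.5.
- Gain per attempt, if only failed objects count as attempts: p x u x e / [1 - p(1 - u)].

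| p | u | e | Total after | Gain per attempt (failed objects only) |
|---|---|---|---|---|
| 1/3 | 0.5 | 2 | 66.0 | +0.40 |
| 1/4 | 0.3 | 1 | 42.9 | +0.09 |
| 1/2 | 0.3 | 1 | 41.8 | +0.23 |
| 1/2 | 0.7 | 3 | 129.8 | +1.24 |

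Over p from 1/4 to 1/2, u from 0.3 to 0.7 and e from 1 to 3, the total ends between 41.8 and 129.8. The per-attempt gain lies between +0.09 and +1.24. With u = 0.3 and e = 1, u(0.5 + e) = 0.45, so the total falls for any trained share.

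**The denominator matters too.** The plan does not define a naming attempt. If all 176 items count and items named at once carry no feature words, the first row gives 44/176 = 0.25 rising to 66/176 = 0.375, a gain of 0.125 instead of 0.40. The third row gives 41.8/176 = 0.2375, a fall.

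**On the plan's effect-size scale.** VI.c divides the post-minus-pre difference by the participant's pre-treatment SD, s. The values s = 5, 10 and 20 are assumed, and the same s is used for pooled and untrained-only totals.

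- Inflation: 24 trained objects gain 1 feature word each and untrained objects gain none. Pooled d = 24/s = 4.8, 2.4 or 1.2; untrained-only d = 0.
- Masking: 24 trained objects become nameable and lose 0.5 each (-12), while 60 untrained objects gain 0.2 each (+12). Pooled d = 0; untrained-only d = 12/s = 2.4, 1.2 or 0.6.

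These cases establish that both directions are possible. They do not estimate what will happen in this trial.

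**The case against.** The strongest reply is that Aim 1b is not worded as a test of transfer. It asks whether participants learn the strategy and behave differently when they cannot name something. Circumlocuting on a trained object that is still unnamed is a use of the strategy, even if some of the content is remembered. Transfer has its own outcomes: Aim 1a measures accuracy on untrained related and unrelated objects, and Aim 2 counts feature words in connected speech. Clinician-supplied features are also only the last cue level.

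Much of this stands. A reader might infer that a positive Aim 1b result would be a predictable false positive, or that the generalization claim rests on it. The documents support neither. Trained objects are expected to become nameable, which pulls the total down, and the plan looks for generalization elsewhere as well.

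What the reply does not do is make the pooled count interpretable. Aim 1a measures accuracy, not feature words, so it cannot show that circumlocution itself reached untrained objects. Aim 2 is a different task. The strategy-knowledge probe records whether components can be listed, not whether they are used.

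**Conclusion.** The point holds as a limit on interpretation. As defined, neither feature-word outcome in Aim 1b can distinguish recalled item content from use of circumlocution on new objects, and the pooled effect may overstate or understate change on untrained objects. This follows from the text alone: no split by object set, trained objects drawn from the assessed items, and features of those objects rehearsed in treatment.

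The size is unknown. Trained-list length, baseline feature counts, their SD and the definition of a naming attempt are all absent, so the figures in the working illustrate direction only. Severity is should-fix: the design, sample, procedures and the other aims are unaffected, and the data needed are already to be collected.

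**What to change.** In VI.c, Aim 1b:

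- Compute both feature-word outcomes separately for trained, untrained related and untrained unrelated objects, as Aim 1a does for accuracy.
- If weekly-probe objects are untreated but repeatedly assessed, report them as their own set and do not merge them with the objects held out for generalization.
- Define a naming attempt, so that the denominator of the per-attempt measure is fixed in advance.
- Base any conclusion that the strategy extends beyond treated items on the untrained objects. Report the trained-object result as possibly including item-specific learning.

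This is a change of wording, best made before results are seen so that the object set is not chosen afterwards. VI.a already provides for verbatim naming attempts, and Phase 1(b) sets each participant's object lists from the pre-treatment assessments. The cost is fewer objects per count and so somewhat less precision. No change to Aim 2 is proposed on this point.
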